Recent studies have suggested a higher incidence of retinal shift in patients treated with gas tamponade compared to those treated with silicone oil. Dell'Omo et al. reported that 41.2% of patients who received gas tamponade experienced retinal displacement compared to only 14.3% of those who received silicone oil (5). Similarly, Codenotti et al. found a 71.4% incidence of retinal displacement in patients who received gas tamponade, compared to only 22.2% in those who received silicone oil (6).

There is currently no local data on the incidence of retinal shift in patients undergoing PPV for RRD using different tamponade agents. Postoperative patient dissatisfaction due to visual distortion despite anatomical success warrants further investigation into factors contributing to retinal shift.

OBJECTIVE

To compare the incidence of retinal shift in eyes undergoing vitrectomy for RRD using gas versus silicone oil tamponade.

OPERATIONAL DEFINITIONS

- **Rhegmatogenous Retinal Detachment (RRD):** Separation of the neurosensory retina from the underlying RPE, associated with subretinal fluid and the presence of at least one full-thickness retinal break. Diagnosis will be based on clinical examination and confirmed intraoperatively.
- **Vitrectomy:** Standard 25-gauge pars plana vitrectomy performed as a primary surgical intervention for RRD. The surgery includes complete vitrectomy, release of vitreoretinal traction, laser photocoagulation or cryotherapy, and fluid-air exchange followed by tamponade with either gas or silicone oil.
- **Retinal Vessel Printings (RVPs):** Hyperautofluorescent lines visible on FAF imaging, corresponding to previous locations of retinal vessels, indicating a shift in retinal position. Presence of RVPs is defined as a positive shift, whereas absence indicates no shift.

- **Refractive Error:** High myopia is defined as a refractive error greater than -6.00 diopters. This will be considered a risk factor for retinal detachment.

HYPOTHESIS

Retinal shift following vitrectomy for RRD is influenced by the type of tamponade used (gas vs. silicone oil).

MATERIALS AND METHODS

Study Design: Randomized controlled trial

Study Setting: Section of Ophthalmology and Visual Sciences, Department of Surgery, Aga Khan University Hospital (AKUH)

Duration of Study: Patients will be recruited after ERC approval and followed up for one month postoperatively. The total duration of the study will be one year.

Sample Size: Based on Dell'Omo et al.'s study (41.2% retinal shift in gas, 14.3% in silicone oil), with 90% power and 5% alpha, the minimum required sample size is 32. However, 80 patients will be included, 40 in each group.

Inclusion Criteria:

Patients with primary RRD

Aged between 18 and 85 years

Undergoing PPV at AKUH

Exclusion Criteria:

Eyes undergoing PPV for causes other than RRD

Previous PPV

Patients with incomplete reattachment

Patients lost to follow-up

Eyes with postoperative findings interfering with FAF, such as ERMs or redetachment

Sampling Technique: Non-probability, consecutive sampling

Randomization: Patients will be randomized into two groups:

Group A (Gas Tamponade): Eyes undergoing PPV with gas (C3F8 or SF6)

Group B (Silicone Oil Tamponade): Eyes undergoing PPV with silicone oil (PDMS)

All surgeries will be performed by vitreoretinal surgeons with at least 10 years of experience. FAF will be performed on postoperative day 10 and at one month using Heidelberg Spectralis. FAF images will be assessed for vertical retinal displacement. The displacement is identified as hyperautofluorescent lines parallel to major retinal vessels

indicating vertical deviation. The images will be independently evaluated by two trained retina specialists masked to the type of tamponade used.

DATA ANALYSIS

Data will be analyzed using SPSS version 23.0. For quantitative variables, age will be reported as either the mean \pm standard deviation or the median with interquartile range, depending on the data distribution. Qualitative variables, including gender, side of eye, type of tamponade, and presence of retinal displacement, will be presented as frequencies and percentages. The incidence of retinal shift between the gas and silicone oil groups will be compared using the Chi-square or Fisher's exact test, as appropriate. A stratified analysis will be conducted to assess potential effect modifiers such as age, gender, and the extent of detachment. Post-stratification comparisons will be made using the Chi-square or Fisher's exact test. A p-value of ≤ 0.05 will be considered statistically significant.

REFERENCES

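### The minimum of 32 for 90% power does not follow from the protocol's own inputs, and the 80 patients planned give about 78% power

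*Protocol*

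**What the plan says.** The Protocol's Sample Size paragraph (Materials and Methods) gives its planning rates as "41.2% retinal shift in gas, 14.3% in silicone oil", attributed to the first of the two tamponade comparisons cited in the introduction. It continues: "with 90% power and 5% alpha, the minimum required sample size is 32. However, 80 patients will be included, 40 in each group". It does not say whether 32 is a total or a number per group, whether the test is one- or two-sided, or which formula was used. It gives no separate power figure for the 80.

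Three other statements bear on the calculation:

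- The Hypothesis section has no direction: "Retinal shift following vitrectomy for RRD is influenced by the type of tamponade used (gas vs. silicone oil)".
- Data Analysis says the incidence in the two groups "will be compared using the Chi-square or Fisher's exact test, as appropriate", and adds: "A p-value of ≤ 0.05 will be considered statistically significant".
- The Exclusion Criteria list "Patients lost to follow-up", along with incomplete reattachment and postoperative findings that interfere with imaging. These can be known only after surgery. No allowance for them appears in the sample size.

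**The concern.** A difference of 41.2% against 14.3% is 26.9 percentage points between two binary outcomes. Ninety per cent power for a difference of that size normally takes more than 50 patients per group, so a minimum of 32 looked too small on either reading.

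The consequence reaches beyond the 32 itself. Because 80 is set against a minimum of 32, a reader or ethics committee will conclude that the trial has at least 90% power with ample reserve. If the true minimum is above 80, the trial has less power than that, and a non-significant result would be taken as stronger evidence of no difference than it is. This paragraph is the only justification the Protocol gives for the size of the trial.

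**Working it through.** **Inputs**

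- p1 = 0.412 (gas), p2 = 0.143 (oil), power 90%, alpha 5%: Sample Size paragraph.
- Two independent proportions, chi-square or Fisher: Data Analysis.
- 40 per group, 1:1: Sample Size paragraph.
- Two-sided testing: my assumption, because the hypothesis has no direction. One-sided results are shown as well.

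Derived quantities: difference d = 0.269; mean proportion (0.412 + 0.143)/2 = 0.2775; A = √(2 × 0.2775 × 0.7225) = 0.6332; B = √(0.412 × 0.588 + 0.143 × 0.857) = √0.3648 = 0.6040.

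**Step 1: try to reproduce the 32 (90% power, per group)**

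Pooled-variance formula, two-sided:

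n = (1.960 × A + 1.2816 × B)² / d² = (1.2411 + 0.7740)² / 0.269² = 56.1, so 57 per group.

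Unpooled formula, two-sided:

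n = B² × (1.960 + 1.2816)² / d² = 52.97, so 53 per group.

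| Formula | Two-sided 5% | Total | One-sided 5% | Total |
|---|---|---|---|---|
| Pooled (chi-square) | 57 | 114 | 46 | 92 |
| Unpooled | 53 | 106 | 44 | 88 |
| Arcsine | 55 | 110 | 45 | 90 |
| Continuity-corrected | 64 | 128 | 53 | 106 |

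Unequal allocation raises the two-sided pooled total (123 at 2:1, 144 at 3:1). A one-sample formula, which would not suit this design, gives 21 to 28. Nothing gives 32 per group or 32 in total.

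The figure 32 appears only when a stated input is changed. One-sided testing at 80% power gives 31.2 per group (unpooled), so 32 per group. The second cited study's rates (71.4% against 22.2%) with a one-sided test at 90% power give 16 per group, so 32 in total. The document does not show which of these, if either, was used.

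**Step 2: power at the sizes the Protocol mentions**

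Power = Φ[(d√n − 1.960 × A) / B]. For n = 40: (1.7013 − 1.2411) / 0.6040 = 0.762, and Φ(0.762) = 0.777.

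| Per group | Reading | Two-sided, pooled | Exact, chi-square | Exact, Fisher |
|---|---|---|---|---|
| 16 | 32 as a total | 39% | 43% | 25% |
| 32 | 32 per group | 68% | 70% | 60% |
| 40 | as planned | 78% | 79% | 71% |

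At 40 per group the unpooled approximation gives 80.4% and the exact power of the Yates-corrected chi-square is 70.5%. One-sided, 40 per group gives 86% (pooled) or 88% (unpooled). Every figure is below 90%.

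**Step 3: what 40 per group can do**

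- With oil held at 14.3%, power is about 90% only when the gas rate is about 46.8%, a difference of 32.5 points instead of 26.9.
- The expected 95% confidence interval half-width at the planning rates is 1.96 × √(0.3648/40) = 0.187, or about 19 points.
- If 10% of eyes were not evaluable (an assumed figure; the Protocol gives none), 36 per group would remain and two-sided chi-square power would be 73%.

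**The case against.** The strongest reply is that the Protocol attaches 90% power to the 32 and states no power for the 80. That is literally so: the 90% for the planned trial is implied. The implication is unavoidable, however, since any trial larger than the true 90% minimum has at least 90% power. The 32 is wrong in any case.

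Second, enrolment was evidently not set by the 32, and 80 is a defensible size. The unpooled formula gives 39.6, so 40 per group, for 80% power. This stands: the trial is near a conventional power level and the error does not make it unsound. It does mean that the stated justification is false.

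Third, sidedness is not stated, and a one-sided test would have 86% to 88% power. That narrows the gap without closing it, and a one-sided test does not fit the hypothesis as written.

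Fourth, Fisher's test is unlikely to be chosen at the planning rates. The smallest expected cell count is 40 × 0.2775 = 11.1, so the usual expected-count rule selects chi-square. I agree that 78% is the lead figure and 71% is secondary. The Fisher figure matters only because the Protocol leaves the choice of test open.

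Finally, the 80 may be meant as evaluable eyes, counted after exclusions. If so, the 73% scenario does not arise. The main result does not depend on it.

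**Conclusion.** The point holds. From the Protocol's own rates, 90% power at two-sided 5% needs 57 per group, 114 in total (53 to 64 per group across formulas). The stated 32 is too low on either reading, and the planned 80 falls short even of the most lenient one-sided requirement of 88. As planned, the trial has about 78% power with the chi-square test, so a type II error of about 22% against the 10% or less implied. With Fisher's test the power is about 71% and the type II error about 29%.

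This rests on the planning rates as printed, 1:1 allocation, 40 evaluable eyes per group and a two-sided test. Relaxing the last assumption changes the size of the shortfall and not the conclusion.

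**What to change.** Remove the minimum of 32 and the associated 90% power claim from the Sample Size paragraph, and replace them with a statement along these lines:

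> Eighty patients (40 per group) give about 78% power with a two-sided 5% chi-square test to detect 41.2% versus 14.3% (about 71% should Fisher's exact test be used). Ninety per cent power would need 57 per group. The expected 95% confidence interval half-width for the difference is about 19 percentage points.

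Also say whether the 80 are counted before or after the postoperative exclusions. If before, give the power at the expected number of evaluable eyes, with the assumed loss stated.

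The cost is a few sentences of protocol text. No additional enrolment is needed to make the statement correct. The only price is that the declared power becomes less favourable.

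### Three of the five exclusion criteria are events that follow the assigned tamponade, so the comparison of retinal shift is no longer between the randomised groups

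*Protocol*

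**What the plan says.** The Protocol gives the design as "Study Design: Randomized controlled trial" and, under Materials and Methods, says "Randomization: Patients will be randomized into two groups", one receiving gas and the other silicone oil. Operational Definitions put the tamponade at the end of the operation: "fluid-air exchange followed by tamponade with either gas or silicone oil".

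The Exclusion Criteria have five entries. Two are settled before surgery: a vitrectomy done for another indication, and an earlier vitrectomy. The other three are "Patients with incomplete reattachment", "Patients lost to follow-up" and "Eyes with postoperative findings interfering with FAF, such as ERMs or redetachment".

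The outcome is binary and is read from fundus autofluorescence (FAF): "Presence of RVPs is defined as a positive shift, whereas absence indicates no shift". On timing, "FAF will be performed on postoperative day 10 and at one month using Heidelberg Spectralis". Data Analysis then compares the two proportions by chi-square or Fisher's exact test. The Protocol gives no expected rate of exclusion and does not say whether an excluded patient would be replaced.

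**The concern.** An exclusion criterion should rest on something known before allocation. Redetachment, an epiretinal membrane (ERM) found after surgery, and loss to follow-up cannot be known then. Incomplete reattachment, read naturally, is a result of the operation. The tamponade is part of that operation, so the frequency of these events, and the kind of eye that suffers them, may differ between gas and oil.

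Applied as written, the rule compares eyes that were successfully reattached, stayed in follow-up and gave a readable image. Randomisation balances the groups as allocated, not these subsets. If the excluded eyes differ between arms in number or in shift status, the test compares groups that are not alike, and both the between-group difference and each arm's incidence can be wrong. The Objective concerns eyes that have vitrectomy for this kind of detachment and is not limited to anatomical successes.

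The rule also discards data. A patient lost, or an eye redetached, after day 10 may already have a gradable image from that visit.

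**Working it through.** **Order of events.** The tamponade is given as the last surgical step (Operational Definitions). FAF follows at day 10 and at one month (Materials and Methods). Postoperative findings that spoil the image, and loss to follow-up, therefore come after the assigned treatment whatever the moment of randomisation, which the Protocol does not state.

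**Inputs from the Protocol.** 40 eyes per group; planning rates 41.2% (gas) and 14.3% (oil), a difference of 41.2 − 14.3 = 26.9 points. The Protocol has no figure for exclusions to reproduce.

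**Assumption.** A fraction of 5% to 20% is excluded in each arm, and the retained eyes show exactly the planning rates.

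**Worst-case bounds.** Let m eyes be excluded per arm and n = 40 − m retained. The lowest difference over all 40 + 40 eyes arises if every excluded oil eye had shifted and no excluded gas eye had. The highest arises in the reverse case.

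- Lowest = (0.269 × n − m) / 40
- Highest = (0.269 × n + m) / 40

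| Excluded per arm | m | n | 0.269 × n | Lowest (points) | Highest (points) |
|---|---|---|---|---|---|
| 5% | 2 | 38 | 10.222 | 8.222/40 = 20.6 | 12.222/40 = 30.6 |
| 10% | 4 | 36 | 9.684 | 5.684/40 = 14.2 | 13.684/40 = 34.2 |
| 15% | 6 | 34 | 9.146 | 3.146/40 = 7.9 | 15.146/40 = 37.9 |
| 20% | 8 | 32 | 8.608 | 0.608/40 = 1.5 | 16.608/40 = 41.5 |

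At 10%, the estimate of 26.9 moves by at most 12.7 points down (26.9 − 14.2) or 7.3 up (34.2 − 26.9).

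**A less extreme scenario, for direction.** Suppose the true risk is the same in both arms, at the mean of the planning rates: (41.2 + 14.3)/2 = 27.75%. If a fraction e1 of shifted eyes and e0 of unshifted eyes are excluded, the risk among retained eyes is

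r(1 − e1) / [r(1 − e1) + (1 − r)(1 − e0)].

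- One arm loses 10% regardless of shift: the retained risk stays at 27.75%.
- The other loses 30% of shifted and 5% of unshifted eyes: 0.19425 / (0.19425 + 0.686375) = 22.1%, a spurious difference of 5.7 points.
- The other instead loses 5% of shifted and 30% of unshifted eyes: 0.263625 / (0.263625 + 0.50575) = 34.3%, a spurious difference of 6.5 points the other way.

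Swapping the arms reverses the signs. These loss rates are also assumptions. The third case implies a total loss of 1 − 0.769375 = 23.1% in that arm, which is heavy.

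**The case against.** **The population of interest may be readable, attached eyes.** The Protocol's introduction is concerned with visual distortion after anatomically successful surgery, so this has some basis. The Objective, however, is not restricted in that way, and choosing patients by a result of treatment forfeits randomisation in any case. What stands is that a readable-eyes comparison deserves a place as a secondary analysis.

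**Incomplete reattachment is not labelled postoperative.** If it were judged during surgery and randomisation came afterwards, that item would be a legitimate exclusion. The Protocol does not say so. The objection touches one of the three items only.

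**A statistical analysis plan could deal with this.** Analysis sets, missing outcomes and patient-flow tables are often left to that document, which is not at hand, and their absence is no defect here. But the exclusion rule is stated in the Protocol, and an analysis plan that kept all randomised patients would contradict it.

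**Some eyes have no outcome to analyse.** In a redetached retina, shift may be undefined rather than missing, and imputing it from arm, age and extent of detachment would invent a value. This stands, and no single imputation model should be required. It also stands that an eye with an ERM that does not interfere with FAF is arguably kept under the present wording.

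**Stronger readings that a reader might infer, and that the Protocol does not support:**

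- *Excluded patients will be replaced until each group reaches 40.* The text neither permits nor forbids this.
- *Twenty of the 26.9 points could vanish at 10% exclusion.* Twenty points is the width of the band; the largest fall is 12.7.
- *Significance is likely to be lost.* One can construct 15/36 vs 5/36 (chi-square p = 0.0085) becoming 15/40 vs 9/40 (p = 0.143). That needs all four excluded oil eyes to have shifted and none of the four gas eyes. If excluded eyes had the retained rates, the chance would be (5/36)^4 × (21/36)^4, about 1 in 23,000. Excluded eyes may well differ from retained ones, but this is an extreme corner, and the reverse corner, 19/40 vs 5/40, gives p = 0.0006.
- *The rule lowers power.* An eye without a readable outcome carries no information whether it is called excluded or missing, so that loss does not come from this wording.

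**Conclusion.** The point holds as a flaw in the stated rule. Three of five exclusion criteria act after the assigned tamponade, so the planned test does not compare the groups as randomised, and day-10 images already in hand may be thrown away. The direction of any bias cannot be known from the Protocol.

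Its size cannot be known either, because no exclusion rate is given. The range of 14.2 to 34.2 points at 10% per arm is a worst-case bound, not a forecast. It rests on the assumed rate and on retained eyes showing the planning rates. The range is modest at 5% but reaches almost to zero at 20%. The conclusion about the design depends on none of these figures. The text should be corrected before recruitment, since outcomes of patients dropped as ineligible may not be recoverable later.

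**What to change.** 1. Limit the Exclusion Criteria to facts known before randomisation, and list incomplete reattachment, loss to follow-up and postoperative findings that interfere with FAF as post-randomisation events.
2. Define the primary analysis set as all randomised patients, by assigned tamponade, and state that patients with these events are not replaced.
3. Use every gradable FAF, including day-10 images from patients later lost or redetached.
4. State how eyes with no readable or definable shift status are counted in the primary analysis, and add best-case and worst-case bounds per arm as a sensitivity analysis. No particular imputation model need be mandated.
5. Report the number of such eyes and the reasons, by arm. The comparison restricted to readable eyes may stay as a secondary analysis.

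The cost is protocol wording and a little extra analysis, with no new patients or procedures. The price in interpretation is that some outcomes can only be bounded.

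### Effect modification is to be assessed by gas-versus-oil tests after stratification, which do not test whether the effect differs between strata

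*Protocol*

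**What the plan says.** Three consecutive parts of the protocol's Data Analysis section bear on this.

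- The aim: "A stratified analysis will be conducted to assess potential effect modifiers such as age, gender, and the extent of detachment".
- The method: "Post-stratification comparisons will be made using the Chi-square or Fisher's exact test".
- The threshold: "A p-value of ≤ 0.05 will be considered statistically significant".

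The only comparison the section defines is the primary one: "The incidence of retinal shift between the gas and silicone oil groups will be compared using the Chi-square or Fisher's exact test, as appropriate". After stratification, the natural reading is the same gas-versus-oil test repeated inside each stratum. No interaction term or test of homogeneity is named. Age and extent of detachment have no cut-points, so the number and size of the strata are unknown.

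**The concern.** Effect modification is a difference between stratum-specific effects. A Chi-square or Fisher test inside one stratum asks only whether the effect there is zero. If one stratum gives p ≤ 0.05 and the other does not, the two effects may still be the same, because the gap in p-values can come from chance or from unequal stratum sizes. Equally, two significant strata can hide effects of quite different size.

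The protocol has not left this method open. It names one, and the one named does not fit the stated aim. At stake are the subgroup statements. A report could say, for example, that tamponade matters only in extensive detachment when the data show no difference between strata.

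**Working it through.** **Inputs.** From Sample Size: planning rates of "41.2% retinal shift in gas, 14.3% in silicone oil", and "However, 80 patients will be included, 40 in each group". From the background before the Objective, as an alternative: "71.4% incidence of retinal displacement in patients who received gas tamponade, compared to only 22.2% in those who received silicone oil". From Data Analysis: the tests and the 0.05 threshold.

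**Assumptions, because the protocol is silent.** Two strata per factor, equal in size, so 40 / 2 = 20 eyes per arm per stratum. The true rates are the same in both strata, so there is no effect modification. Tests are two-sided. *As appropriate* means Fisher when any expected count is below 5 and otherwise Pearson Chi-square; *Fisher only* is shown alongside.

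**The plan's own figure.** The protocol gives none for the stratified analysis. Its sample-size statement, "with 90% power and 5% alpha, the minimum required sample size is 32", does not enter here. It also does not reproduce:

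n per arm = [1.96·√(2·0.2775·0.7225) + 1.2816·√(0.412·0.588 + 0.143·0.857)]² / 0.269² = (1.241 + 0.774)² / 0.0724 ≈ 56.1, so 57 per arm.

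That is a separate matter. The planned 80 is what sets the stratum size.

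**Step 1: power in one stratum.** Sum the exact binomial probabilities of all 20-versus-20 tables that give p ≤ 0.05. Call the result π.

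**Step 2: split verdict for one factor.** The strata contain different eyes, so P(exactly one significant) = 2π(1 − π).

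| True rates, same in both strata | Test | π | Exactly one significant |
|---|---|---|---|
| 41.2% vs 14.3% | as appropriate | 0.479 | 2 × 0.479 × 0.521 = 0.499 |
| 41.2% vs 14.3% | Fisher only | 0.368 | 2 × 0.368 × 0.632 = 0.465 |
| 71.4% vs 22.2% | as appropriate | 0.894 | 2 × 0.894 × 0.106 = 0.190 |
| 71.4% vs 22.2% | Fisher only | 0.824 | 2 × 0.824 × 0.176 = 0.290 |

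At the planning rates with the as-appropriate rule, both strata are significant in 23% of trials and neither in 27%. Unequal strata raise the split: 58% with 28 + 12 eyes per arm and 62% with 30 + 10 (Fisher only, 51% and 54%).

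**Step 3: three factors.** The factors divide the same 80 eyes, so their results are correlated and Step 2 cannot simply be compounded. Simulating three independent 50:50 factors gives the chance of at least one split. The no-effect case uses the mean planning rate, (41.2 + 14.3) / 2 = 27.75%, in both arms.

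| True rates | Strata drawn at random, 50:50 | Strata fixed at exactly 20 per arm |
|---|---|---|
| 41.2% vs 14.3% | about 73–76% | about 71–75% |
| 71.4% vs 22.2% | about 35–43% | about 34–48% |
| 27.75% in both | about 15–17% | about 12–20% |

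Each range spans the two test rules. Repeat runs move the figures by about a point.

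**Step 4: an illustration.** Suppose one stratum has 8/20 shifts with gas and 2/20 with oil, and the other has 8/20 and 3/20.

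- Stratum 1: χ² = 40 × (8·18 − 2·12)² / (20·20·10·30) = 4.80, p = 0.03.
- Stratum 2: χ² = 40 × (8·17 − 3·12)² / (20·20·11·29) = 3.13, p = 0.08.
- Between strata: the odds ratios are 6.0 and 3.8. The difference in log odds ratios is 0.463 with standard error √(0.764 + 0.600) = 1.168, so z = 0.40 and p = 0.69.

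One eye separates a significant stratum from a non-significant one, with no evidence that the effects differ.

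**Step 5: the right test.** A Wald test on the difference in log odds ratios (0.5 added to each cell, 20 per arm per stratum) signals falsely in about 3% of trials at the planning rates. Its power is about 18–24% if the planning effect exists in one stratum only, and about 75% for a full reversal.

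**The case against.** A reader might infer that the trial, run as written, is more likely than not to report a false effect modifier. The documents do not support that. A majority chance arises only at the planning rates; at the larger effect the protocol also cites it is about 35–43%, and with no effect about 15–17%. These are also probabilities of a pattern. The protocol states no rule that a split between strata will be read as effect modification, so the step to a reported claim is an inference. Nor are split p-values strictly the expected result for a given factor: the chance is roughly even at the planning rates and well below that at the other rates.

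Other points have force. Equal strata and independent factors are assumptions. The wording about post-stratification comparisons does not literally say that tests are run inside each stratum. With three factors of at least two levels there would be at least six tests at 0.05, but multiplicity rules for subgroup looks are commonly left to a statistical analysis plan, so their absence is not a defect here. The sole objective is the overall comparison, and the remedy will seldom detect real modification at this sample size.

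None of this removes the mismatch. The stratified tests are the only stated means of assessing modifiers, no other reading of a two-group test after stratification is natural, and nothing elsewhere in the protocol supplies the missing comparison between strata. A statistical analysis plan could add an interaction test, but the protocol sentence would still name the wrong method.

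**Conclusion.** The point holds as a mismatch between aim and test. Under an identical true effect, and assuming two equal strata per factor, a split verdict occurs in about 47–50% of trials per factor at the planning rates and 19–29% at the other cited rates. For at least one of three independent factors the figures are about 73–76% and 35–43%, and about 15–17% with no effect at all. The plan invites readers to take such a split as effect modification, though it does not compel them to. The damage is confined to subgroup conclusions; the primary gas-versus-oil comparison is untouched.

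**What to change.** In Data Analysis, replace the post-stratification tests as the means of assessing effect modification with one tamponade-by-factor test per factor: an interaction term in logistic regression, or a Breslow-Day or exact test of homogeneity of odds ratios. Report stratum-specific risk differences with 95% confidence intervals as exploratory. State that no claim of effect modification will rest on significance within a stratum.

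This takes a few sentences and changes nothing in recruitment, data collection or the primary test. The downside is low power with 80 eyes (about 18–24% if the effect exists in one stratum only, under the assumptions above). The text should say so, and should say that a non-significant interaction does not show that the effect is the same in all strata.
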